#### 4.1.4 Discontinuations

Participants who discontinue the study prematurely (i.e., dropout) will not be replaced. A temporary discontinuation exceeding 14 consecutive days or 21 days overall results in a permanent discontinuation. If unexpectedly high dropout rates occur (e.g., due to COVID-19), the number of randomized participants may be increased by up to 20%. For further details with respect to the analysis of dropouts refer to the Section 4.1.3 on handling of Missing Data.

A participant may withdraw from the study at any time at his/her own request or may be withdrawn at any time at the discretion of the investigator for safety, behavioral, or compliance reasons. This includes cases where, in the investigator's opinion, continued participation in the study would be harmful to the participant's well-being. This is expected to be uncommon. At the time of discontinuing from the study, if possible (if the participant is not lost to follow-up and if the health status of the participant allows), Visit 15 should be conducted as early discontinuation visit, followed by safety follow-up (Visit 16). Data collected at early discontinuation visits will be handled as follows: If a valid DRSS assessment is available from the early discontinuation visit, this value will be considered for analyses for the respective visit. Other variables assessed at early discontinuation visits will be listed for individual follow-up but not be considered for summary statistics.

Participants who permanently discontinue study treatment are invited to continue to attend all protocol-specified study visits. Values assessed at visits after discontinuation from study treatment will be listed for individual follow-up but not be considered for summary statistics. All values assessed after study treatment discontinuation will be flagged in the listings.

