7.1 Discontinuation of study intervention

7.1.1 Permanent discontinuation

In rare instances, it may be necessary for a participant to permanently discontinue (definitive discontinuation) study intervention. If study intervention is permanently discontinued, an End-of-Treatment visit should be performed in line with Visit 15. The participant remains in the study for continued assessment of study outcomes following the visit schedule in section 1.3.

Unscheduled visits may be performed as deemed appropriate by the investigator, in particular in case of withdrawal because of an adverse event.

Participants *must* be withdrawn from the *study intervention* for any of the following reasons:

- Increases in transaminases as described in Table 10-3 (confirmed by analysis of two blood samples; additional laboratory examinations may be performed if necessary):
- Safety concerns for a participant by the investigator or the sponsor, e.g. due to obvious non-compliance.
- Pregnancy (see Section 8.3.5 for details)
- Temporary discontinuation exceeding 14 consecutive days or 21 days overall

Participants *may* be withdrawn from the *study intervention* for any of the following reasons:

- Repeated incidents of relevant hypotension or tachycardia
- Repeated temporary discontinuation of study intervention
- Vision threatening complication or progression to PDR

Necessity to withdraw the participant from the study will be assessed case by case by the investigator.

09 FEB 2023 Page: 45 of 95

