#### 4.1.2 End of Treatment

Beside the Visit 15 EoT, the EoT values will also be derived to account for eCRF entry errors. The EoT value is the value of the visit at the last treatment day. In case no visit occurred at the last treatment day, the EoT value is the value of the first visit after last treatment.

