#### 4.1.3 Missing Data

For handling of missing data for the primary efficacy endpoint, see Section 5.3.2.

Statistical analysis will be based on the available data. Analysis will be performed considering all valid data observed for the respective analysis sets. All missing or partial data will be presented in the subject data listing as they are recorded on the CRF.

Date of first dose of study intervention is defined as the date of first dose from the appropriate CRF page capturing the study intervention (runcaciguat or placebo) if this date is complete. Date of last dose of study intervention is defined as the date of last dose from the appropriate

CONFIDENTL	٩L
COLUMN TO DIVIN	

CRF page capturing the study intervention if this date is complete. If the first and the last dose dates are missing or incomplete, we will consider the following scenarios for imputation of missing dates:

First dose date is missing or incomplete	Imputation rule	
Only day of first dose date is missing	Impute the first dose date as maximum of the	
	date of randomization and first day of month.	
Month and day of first dose date are missing	Impute the first dose date as randomization date.	
First dose date is completely missing but last	Impute the first dose date as randomization date	
dose date is available	but no later than the date of last dose.	
First dose date and last dose date are missing	Impute the first dose date as randomization date if tablet boxes were dispensed and if these tablet boxes were not returned unused.	
Last dose date is missing or incomplete	Imputation rule	
Only day of last dose date is missing	
 
Impute the last dose date using last day of the month.
 
Derive last dose date as minimum of (imputed last dose date, the date of death, the last visit date before follow-up) but no earlier than the date of first dose.
 
	
Month and day of last dose date is missing	
 
Impute the last dose date using last day of the year.
 
Derive last dose date as minimum of (imputed last dose date, the date of death, the last visit date before follow-up) but no earlier than the date of first dose.
 
	
Last dose date is completely missing but first dose date is available or can be imputed	Impute last dose date as minimum of (the date of death, or the last visit date) but no earlier than the date of first dose.	

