## 4.4.2 Fluorescein angiography

Change in leakage area on FA: The anatomical state of the retinal vasculature of the study eye (transit eye) and the fellow eye (non-transit eye) will be evaluated by FA. The angiographic images will be evaluated by a study ophthalmologist for individual safety decisions. Fluorescein leakage area will be evaluated using FA. Descriptive statistics including box plots will be provided for the change in quantitative FA assessments from baseline to Week 24 and 48 by treatment group using geometric and arithmetic means as defined in Section 4.1.

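### SAP 4.1.4 keeps every measured variable except DRSS from the early discontinuation visit out of summary statistics, and no section assigns the EoT value derived in SAP 4.1.2 to a table; FA leakage is hit hardest

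*SAP*

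**What the plan says.** SAP 4.1.4 sets three rules for data at or after an early stop.

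- DRSS at the early discontinuation visit: "If a valid DRSS assessment is available from the early discontinuation visit, this value will be considered for analyses for the respective visit".
- Everything else at that visit: "Other variables assessed at early discontinuation visits will be listed for individual follow-up but not be considered for summary statistics".
- Participants who stop treatment but keep attending: "Values assessed at visits after discontinuation from study treatment will be listed for individual follow-up but not be considered for summary statistics".

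SAP 4.1.2 separately defines an EoT value, taken from the visit on the last treatment day. Failing that, "In case no visit occurred at the last treatment day, the EoT value is the value of the first visit after last treatment". Its stated purpose is narrow: "the EoT values will also be derived to account for eCRF entry errors".

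The general rule in SAP 4.1.3, repeated in Protocol 9.4.1, is broad: "Analysis will be performed considering all valid data observed for the respective analysis sets".

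On data collection, Protocol 7.1.1 says: "If study intervention is permanently discontinued, an End-of-Treatment visit should be performed in line with Visit 15". Protocol 7.2 asks for Visit 15, where possible, when someone leaves the study. Under Table 1-4 of the Protocol, Visit 15 includes BCVA, OCT, FA, ECG, blood pressure and laboratory tests. Leakage is summarised as "change in quantitative FA assessments from baseline to Week 24 and 48 by treatment group" (SAP 4.4.2).

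**The concern.** The plan asks for a full set of measurements when a participant stops, then summarises only one of them. The SAP gives no reason for separating DRSS from the other variables taken at the same visit.

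Stopping can be linked to the outcomes concerned. Under Protocol 7.1.2 a confirmed eGFR fall of 40% or more ends treatment. Hypotension and vision-threatening complications are also listed among the grounds for stopping. A Week 48 mean restricted to participants still on treatment is therefore a selected mean, and the selection may differ between arms.

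Change in visual acuity and change in leakage area sit under the primary objective as other endpoints (SAP Table 1-1). They would be read alongside DRSS when the PoC result is interpreted.

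**Working it through.** **1. What is lost.** Take a participant who stops before Week 48.

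- *Leaves treatment and study together.* The early discontinuation visit is Visit 15. DRSS is used; the rest is listed only.
- *Stops treatment but stays in the study.* Values from visits after the stop are listed only. Table 1-4 schedules no dosing at Visit 15, so an EoT visit run on that pattern will normally follow the last dose and fall under this rule. If the visit falls on the last treatment day, the SAP does not say which row takes the value.

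**2. What remains, by variable.**

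| Variable | Scheduled assessments (Protocol Tables 1-2 to 1-4) | Left in summaries after an early stop |
|---|---|---|
| FA leakage | Screening, Visit 12 (Week 24), Visit 15 (Week 48) | Stop before Week 24: nothing post-baseline. Stop between Weeks 24 and 48: Week 24 only |
| BCVA | Post-baseline at Visits 8, 10, 12, 13, 14, 15, 16 | On-treatment visits before the stop |
| CRT (OCT), laboratory tests | Every visit | On-treatment visits before the stop |
| ECG | Most visits | On-treatment visits before the stop |
| Vital signs | Every visit | On-treatment visits before the stop. SAP 4.5.5 spells out titration-phase visits only; later rows rest on the general by-visit rule in SAP 4.1.1 |

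**3. Does the EoT value fill the gap?** For most early stoppers, the first visit after last treatment is the visit whose non-DRSS values SAP 4.1.4 only lists. SAP 4.2 to 4.6 assign the derived EoT value to no summary. It is defined but unused.

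**4. Frequency tables.** For unscheduled data, SAP 4.1.1 excludes values from both summary statistics and frequency tables. SAP 4.1.4 names summary statistics only. Whether the liver-criteria table (SAP 4.5.3) and the eGFR-decrease table (SAP 4.5.4) count EoT-visit values is not stated.

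**5. The plan's own figure.** The one design figure is a probability of PoC of at least 90%. Exact enumeration with 40 per arm, response rates of 10% and 35% and Beta(0.5, 0.5) priors gives 90.3%, so it is reproduced. It does not move, because DRSS from the early discontinuation visit is already used.

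**6. Possible size for BCVA (assumed inputs).** The documents give no SD, effect or dropout rate for these variables. Let d be the fraction of an arm whose stopping value is left out, and g the gap in letters between the values kept (mean m) and those left out. The mean with them included is (1 − d)m + d(m − g) = m − dg, so the arm mean shifts by d × g.

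- d = 5%, g = 2: 0.05 × 2 = 0.10 letters
- d = 10%, g = 5: 0.10 × 5 = 0.50 letters
- d = 18/98 = 18.4%, g = 10: 0.184 × 10 = 1.84 letters

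The difference between arms shifts by the difference of the two products, which is zero if d × g is equal in both arms.

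The 18.4% comes from 98 randomised and 80 evaluable. It is not a dropout rate: non-evaluability has other causes, and someone who stops early can still be evaluable for DRSS through LOCF or as a non-responder.

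**7. Time window.** SAP 4.2.2 accepts an EoT DRSS within 4 weeks of treatment discontinuation. The half-life is about 14 to 21 hours (Protocol section 2). Four weeks is 672 hours: 672/21 = 32 to 672/14 = 48 half-lives. Five half-lives are 5 × 14 = 70 hours (2.9 days) to 5 × 21 = 105 hours (4.4 days). The 4-week limit is usable for retinal structure, but is too long for blood pressure, ECG, eGFR or laboratory values meant to reflect treatment.

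**The case against.** The strongest reply is that this is a deliberate on-treatment description of low-tier endpoints. BCVA and leakage are other endpoints, analysed descriptively with no decision rule, and restricting to on-treatment values resembles the while-on-treatment strategy chosen for DRSS. The first part stands and limits the weight of the point. The second only partly helps: the DRSS strategy carries an early stopper's last value forward into the Week 48 analysis, whereas here the participant drops out of the later rows.

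Four stronger readings are tempting, and the documents do not support them.

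- *That safety reporting leaves these participants out.* TEAEs are counted to 28 days after the last dose (SAP 4.1.5). SAP 4.5.2 tabulates AESIs and TEAEs leading to discontinuation. VTCs, including a BCVA loss of 10 letters or more, are recorded continuously and analysed by Kaplan-Meier (SAP 4.3.1). Only summaries of measured values are affected.
- *That SAP 4.1.4 contradicts or cancels SAP 4.1.2.* SAP 4.1.2 never says the EoT value enters a table, so this is a missing link. Table layouts are in a separate TLF specification, which is not available here.
- *That the summaries become completer analyses.* Values from on-treatment visits before the stop remain. Only late rows are restricted, and only leakage can lose a participant altogether.
- *That a real acuity difference between arms would vanish.* This needs poor stopping values in one arm and not in the other. The documents give neither.

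The objection that a 4-week EoT value could dilute haemodynamic or renal effects is right. So is the point that VTC treatment may alter BCVA and CRT (Protocol 8.1.2 mentions anti-VEGF). Both shape the fix.

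**Conclusion.** The point holds as a limited, inexpensive improvement to the descriptive analyses. SAP 4.1.4 states a rule that discards collected, non-DRSS measurements from the stopping visit. The consequence is certain for leakage in anyone stopping before Week 24, even if the FA called for at the EoT visit was done. For BCVA, CRT, laboratory values, eGFR, vital signs and ECG, the stopping value is lost and Week 48 rows cover participants still on treatment.

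The size cannot be computed from the documents. The range of about 0.1 to 1.8 letters for a BCVA arm mean rests on assumed fractions of 5% to 18.4% and assumed gaps of 2 to 10 letters. An imbalance between arms is possible but not demonstrated. The primary endpoint, the PoC rule and the event-based analyses do not change.

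**What to change.** In SAP 4.1.4, leave the by-visit rows as they are and add one end-of-treatment row (change from baseline) per table, using the EoT value from SAP 4.1.2.

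- FA leakage, BCVA and CRT: include assessments within 4 weeks of the last dose, the limit already used for DRSS. Flag values taken after treatment of a VTC.
- Vital signs, ECG, eGFR and laboratory values: use a shorter window of about 5 half-lives (roughly 3 to 4 days), or show days since last dose.
- Liver-criteria and eGFR-decrease frequency tables: state that EoT-visit values are counted.

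The cost is SAP wording and one programmed row per table; the data are already collected under the protocol. The drawback is that the row mixes treatment durations and times since last dose, so it needs a footnote saying so.

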#### 4.1.5 Adverse events

For the purpose of date imputation, the treatment follow-up period date is defined as the last available visit date including unscheduled visits after the EoS visit.

If the start or stop time of the AE is missing completely, the duration of the AE will be calculated based on the start and stop date. If only the start or stop minutes are missing, the duration will be calculated based on the dates and hours. If the start date is partially missing, the first day of that month will be used when only the day is missing. If the stop date is partially missing, the last day of the month will be used when only the day is missing. If both the day and the month are missing, the date will be missing.

Imputed dates will only be used for summary tables. Listings will contain the original entries.

TEAEs are AEs that occurred after first dosing and existing pre-dose AEs that worsened in severity post-dose during the main treatment period until 28 days after the last dose of the study drug.

To determine if an AE is treatment-emergent the following rules will be applied considering a worst-case scenario:

- If the date and time of AE start are completely missing, the AE will be considered as treatment-emergent unless the stop date and time suggest otherwise
- If the time of AE start is missing, but the start date (day, month, and year) of the AE is known, the AE will be considered as treatment-emergent if the AE start date is between the date of treatment start and the date of treatment end plus 28 days (both included), unless the stop date and time of the AE (or other information) suggest otherwise
- If the time and day of AE start are missing, but the month and year is known, the AE will be considered as treatment-emergent if the month of AE start is between the month of treatment start and the month of treatment end date plus 28 days (both included), unless the stop date and time of the AE (or other information) suggest otherwise
- If the time, day, and month of AE start are missing, but the year is known, the AE will be considered as treatment-emergent if the year of AE start is between the year of treatment start and the year of treatment end date plus 28 days (both included), unless the stop date and time (or other information) suggest otherwise.

#### 4.1.6 Medical history

Completely or partially missing end dates will not be imputed. For imputation of missing diagnosis date, the following rules will be applied:

Page: 17 of 35

MH start date	Imputation rule
Only the day is missing	Impute the date as minimum of first day of the
	month and treatment start date - 1
Month and day are missing	Impute the date as minimum of July 1 st of the
	year and treatment start date - 1
Start date is completely missing but parts of the	Impute the start date as minimum of (July 1st of
stop date are available, or medication is ticked	the year of the initial visit and the treatment start
as ongoing	date - 1)

#### 4.1.7 **Prior and concomitant medication**

Generally, partially missing prior and concomitant medication start dates will be set to the earliest logically possible date. Partially missing stop dates will be set to the latest logically possible date. For prior and concomitant medication, the following imputation rules will be applied:

Start of medication is missing	Imputation rule
Only the day is missing	Impute the date as first day of the month.
Month and day are missing	Impute the date as January 1 st of the year.
Start date is complete missing but parts of the stop date are available, or medication is ticked as ongoing	Impute the start date as minimum of (January 1 st of the year of the initial visit and the previous or concomitant medication stop date), since information is available that the patient took previous or concomitant medication, and it can be assumed the patient was on medication already at study start.
Stop of medication is missing	Imputation rule
Only the day is missing	Impute the date as minimum of date of death, date of last contact and day of incomplete date replaced by last day of the month.
Month and day are missing	Impute the date as the minimum of date of death, date of last contact and day and month of incomplete date replaced by December 31 st .
Stop date is complete missing but medication is ticked as ongoing	Impute the date as the minimum of date of death and date of last visit.

#### 4.1.8 Laboratory and Biomarker values

Regarding the imputation of PK concentrations below the LLOQ see Section 4.6.1.

Descriptive statistics at any time will only be calculated if at least 2/3 of the individual data were measured and were above the LLOQ and below the ULOQ. For the calculation of descriptive statistics, a data point below LLOQ will be substituted by one half of this limit, a data point above ULOQ will be substituted by ULOQ.

In tables showing descriptive statistics, where values below LLOQ or above ULOQ are included, these statistics will be marked. Differences (i.e., changes from baseline) will not be calculated if both measurements are substituted.

Values incorporated as '< x' into the database will be substituted by x/2, values incorporated as '> y' will be substituted by y itself for calculation of summary statistics.

In case that more than one normal range is available for a laboratory parameter, all normal ranges will be provided in the tables and the widest normal range will be displayed in the figures. No normalization of laboratory values will be performed.

CONFIDENTIAL
--------------

If not stated otherwise, summary statistics (minimum and maximum excluded) (and figures) focused on mean values will be provided if evaluable data of  $\geq$  3 participants are available. Minimum and maximum will be provided if at least one evaluable data point exists.

## 4.1.9 Data Rules

Summary statistics of continuous variables assumed as normally distributed will be provided including *absolute* changes from baseline as described in Section 4.1.1. Absolute changes from baseline will be calculated as post-dose value minus baseline value unless noted otherwise. In case of continuous variables assumed to be log-normally distributed summary statistics will comprise *relative* changes from baseline. Relative changes from baseline will be calculated as post-dose divided by baseline value unless noted otherwise. Baseline is defined as the last pre-dose assessment before first study intervention.

In case of replicate measurements for one visit mean values of the unrounded original values will be calculated by participant and visit. Summary statistics of these mean values will be provided.

Box plots will be displayed with whiskers of 1.5 times the interquartile range (i.e., third quartile minus first quartile) above the third quartile, and a distance of 1.5 times the interquartile range below the first quartile. All data points above or below the whiskers will be printed separately.

## 4.2 Primary Endpoint Analysis

## 4.2.1 Definition of Endpoint

The primary endpoint is ' $\geq$  2-step improvement in DRSS at 48 weeks of treatment in the study eye'.

The proportion of patients with ' $\geq$  2-step improvement' will be denoted as  $\pi_{ACT}$  within the runcaciguat treatment arm and as  $\pi_{PLC}$  within the placebo treatment arm.

To assess the efficacy, the retinal morphology will be investigated by 7-field CFP used for assessment of the DRSS by a central reading center. The images of the screening visit of both eyes will be used as part of the eligibility assessment regarding the severity of DR.

## 4.2.2 Main Analytical Approach

For the primary analysis, the last observation before missing DRSS values will be carried forward (LOCF) to impute missing values if the participant dropped out after visit 9 (week 12) and the EoT DRSS assessment was performed within 4 weeks of treatment discontinuation (*while on treatment strategy*). If the last measured DRSS score already showed an improvement by  $\geq 2$  steps at the last measurement prior to the missing assessment, the participant will be considered a responder for the primary endpoint. Otherwise, the participant will be considered a non-responder. If the participant dropped out after visit 9 (week 12) and the EoT DRSS assessment was performed more than 4 weeks after treatment discontinuation the last available DRSS assessment prior to treatment discontinuation will be used (LOCF) (*while on treatment strategy*). Participants who dropped out before visit 9 (week 12), or who had a VTC in the study eye prior to the missing assessment will be considered non-responders regardless of the DRSS level (*composite variable strategy*).

Treatment groups will be runcaciguat and placebo, actually administered dose levels will not be considered for this analysis.

Primary efficacy analyses will be performed on the PPS and will include only study intervention compliant participants (*principal stratum strategy*). In addition, sensitivity analyses will be performed on the FAS. Further analyses may include a separate analysis for each runcaciguat maintenance dose level that was reached during titration (on the PPS). Participants will be analyzed according to the treatment (i.e., runcaciguat or placebo) they actually received.

The study will be analyzed using Bayesian inference with non-informative priors. PoC shall be defined as fulfillment of the following criteria:

•  $P(\pi_{ACT} - \pi_{PLC} > 0 | data) \ge 0.9$ i.e., the posterior probability that the difference between  $\pi_{ACT}$  and  $\pi_{PLC}$  is greater than 0 (clinical activity) given the data observed in the study needs to be 90% or more,

and

•  $P(\pi_{ACT} > 0.25 | data) \ge 0.5$ i.e., the posterior probability that  $\pi_{ACT}$  is greater than 0.25 (clinical relevance) given the data observed in the study needs to be 50% or more.

95% credible intervals will also be presented for  $\pi_{ACT}$  and for  $\pi_{PLC}$ 

The response criterion is assumed to be binomially distributed within each treatment arm. For the Bayesian evaluation, a Jeffrey's prior (i.e., a Beta (0.5,0.5)-prior) will be used. Under these assumptions, the posterior distribution for the parameter  $\pi$  will be a Beta (k+0.5, n-k+0.5)-distribution, where

- k is the number of patients with DRSS  $\geq$  2-step improvement within the respective study arm and
- n is the number of patients within the respective study arms.

In order to demonstrate the clinical activity, the posterior distribution of  $\pi_{ACT} - \pi_{PLC}$  will be used to establish the posterior probability that  $\pi_{ACT} - \pi_{PLC} > 0$  by using a Monte-Carlo-approach.

The posterior distribution for clinical relevance can be directly evaluated from the Beta (k+0.5, n-k+0.5)-distribution in the runcaciguat arm.

The Bayesian posterior probabilities  $P(\pi_{ACT} - \pi_{PLC} > 0 | data)$  and  $P(\pi_{ACT} > 0.25 | data)$  will be calculated using a Monte Carlo Approach: Within each arm, 100000 samples will be obtained from the posterior distribution (i.e., a Beta (k+0.5, n-k+0.5)-distribution). As a seed for random number generation, a fixed seed will be used. This seed has to be included into the program output, in order to ensure that the analysis can be repeated.

From these random samples, the following quantities will be obtained:

- Estimation of  $P(\pi_{ACT} \pi_{PLC} > 0 | data)$ :
  - Difference  $\delta^{(i)}$  between the ith sampled proportion in the active arm  $(=\pi_{ACT}^{(i)})$  and the ith sampled proportion in the placebo arm  $(=\pi_{PLC}^{(i)})$ :  $\delta^{(i)} = \pi_{ACT}^{(i)} - \pi_{PLC}^{(i)}$
  - Relative frequency of the event ' $\delta^{(i)} > 0$ ' within the samples of  $\delta^{(i)}$
- Estimation of  $P(\pi_{ACT} > 0.25 | data)$ :
  - Relative frequency of the event ' $\pi_{ACT}^{(i)} > 0.25$ ' within the samples of  $\pi_{ACT}^{(i)}$

